9.2.5 Study Place

Registry patients will be enrolled in the EU only. It is foreseen that approximately 40 suitable centres in the European Union (EU) will be involved and additional sites may be added, as required. The final list of countries will depend on the Lamzede authorisation and capability of the site to administer the treatment. Indicatively, the following countries will be involved: Germany, Denmark, Sweden, Norway, The Netherlands, Austria, Spain, France, UK, Italy, Belgium and Poland.

Study Duration

The overall duration of the study is not defined. The enrolment for participation in the Registry will occur for an indefinite period. The duration of the observational period for each patient will be of 15 years. The end of the study is defined as the last visit of the last patient in the study.

9.2.6 Study Plan

The Registry will be conducted under conditions of routine clinical practice, without Registry-mandated diagnostic procedures and assessments that can be considered as outside of routine clinical care by the treating physician. Data collection will coincide with routine care visits only according to the judgement of the treating physician. Patients' data collection including retrospective data will be performed.

If applicable in accordance with routine clinical practice, the following schedule of assessments is recommended, as presented in Table 1 and previously described in section 9.1 concerning study design.

Since this is an observational study capturing only the outcomes of routine clinical practice, participation in the Registry will not change the patient/physician relation, nor influence the physician's drug prescription or therapeutic or other management of the patient.

Lamzede has to be administered in accordance with the current Lamzede SmPC and in line with usual clinical practice.

If further medicinal products will be applied besides Lamzede® for the treatment of alpha mannosidosis all medicinal products have to be administered in accordance with their respective SmPCs and in line with usual clinical practice.

Clinical Protocol Number: CLI-LMZYMAA1-12

Clinical Protocol Version Number: 8.0

Date: 01 February 2019

Table 1 Schedule of Assessments to be reported (Flow-Chart).

Procedure	Registry Inclusion visit	Registry Baseline visit	Unscheduled Follow-up Routine	Six-month Follow-up Routine	Yearly Follow-up Routine
	(approx 7 days)	(Time 0)	Clinical Visits ¹	Clinical Visits ²	Clinical Visits
Administrative					
Informed consent form	Х	X ³			
Inclusion/exclusion	Х	X ³			
criteria					
Medical and disease	X	X ³⁻⁴			
history (including					
disease onset, residual					
enzymatic activity,					
genotype mutations,					
bone marrow					
transplantation) and					
concomitant illnesses					
Previous and		X4	X	X	X
concomitant					
medications, including					
Lamzede in hospital or					
home infusion setting					
Concomitant procedures	Х	Х	X	X	X
Physical examination ⁵		Х	X	X	X
(Vital signs and					
anthropometric					
measurements, including					
rate of growth)					
Demographics	X	X ³			
Administration of medica	ation			•	
Lamzede therapy, in		Х	X	X	X
hospital or home					
infusion setting ⁶					
Assessments ⁷					
Anti-velmanase alfa-IgG		Х	X		X
antibody (ADA) ^{7a}					
Standard haematological		Х	X		X
tests ^{8a}					
Laboratory chemistry ^{8b}		Х	X		X
Oligosaccharides in		Х	X		X
serum ^{7a}					

Clinical Protocol Number: CLI-LMZYMAA1-12

Clinical Protocol Version Number: 8.0

Date: 01 February 2019

Procedure	Registry Inclusion visit (approx 7 days)	Registry Baseline visit (Time 0)	Unscheduled Follow-up Routine Clinical Visits ¹	Six-month Follow-up Routine Clinical Visits ²	Yearly Follow-up Routine Clinical Visits
Serum Immunoglobulin class G, A, M ^{7a}		Х	X		X
Three-minute stair climbing test (3MSCT) ⁹ , when applicable		Х			X
Six-minute walk test (6MWT) ⁹ , when applicable		Х			X
Two-minutes walk test (2MWT) ¹⁰ , when applicable		X			X
Forced vital capacity (L and % of predicted)		Х	X		X
Electrocardiogram		Х	X		X
Hearing test (PTA)		Х	X		
Infections (including length and antibiotics requirement)		Х	X		X
Psychotic events		Х	X		X
Adverse Events /Adverse Drug Reactions ¹¹	X	Х	Х	Х	X
Health Assessment Questionnaires					
EQ-5D-5L		Х			X
Zarit Burden Interview		Х			X
CHAQ		Х			X
Behavior Checklists ¹²		Х			X

Abbreviations: ADA, anti-velmanase alfa-immunoglobulin G (IgG) antibody; CHAQ, Childhood Health Assessment Questionnaire; EQ-5D-5L, European Quality of Life Five Dimension Five Level Scale; L, litre; PTA, pure tone audiometry

1. Unscheduled follow-up visits can be performed at, but not limited to, three months after Lamzede treatment start, or whenever deemed appropriate according to treating physician's judgement for patients that start Lamzede treatment within one year prior to Registry inclusion.

2. Additional follow-up visit after six months is highly recommended for patients that start Lamzede treatment within one year prior to Registry inclusion.

- 3. If not taken or collected at Registry Inclusion visit.
- 4. Patients' retrospective data may be collected at the time of Registry enrolment if available. Baseline visits are recommended to be repeated for those patients who will start Lamzede therapy during the course of the study, before therapy is initiated.
- 5. Physical examination to collect vital signs, anthropometric measurements like height, weight, rate of growth and the ability to perform the endurance test at the study visit.
- 6. If applicable, information regarding weekly Lamzede therapy received by the patient need to be recorded within all the Registry duration

Clinical Protocol Number: CLI-LMZYMAA1-12	
Clinical Protocol Version Number: 8.0	Date: 01 February 2019

- 7. All assessments mentioned in the above table will be collected only if considered necessary and available as part of routine clinical practice by the treating physician and no additional tests specific to the Registry will be done.
 - 7a. The markers (oligosaccharides in serum, IgG, IgA and ADA) will not be evaluated by a central laboratory for German patients only, while markers testing will take place according to local routine clinical practice in Germany.
- The markers oligosaccharides in serum, IgG, IgA and ADA) will be evaluated through a central laboratory in EU countries other than Germany.
- 8. Standardtest for haematology and chemistry assessed by local laboratory if available per clinical practice of the site:
 - a. Haemoglobin, haematocrit, platelet count, red blood cells, white blood cells with differential count (band forms, segment forms, neutrophils, eosinophils, basophils, monocytes, lymphocytes) (all expressed in % as well as in absolute numbers). Blood smear for leukocytes detection by electronic microscopy may be done at the treating physician's discretion.
 - b. Biochemistry: Serum electrolytes (sodium, potassium, calcium, inorganic phosphate), creatinine, creatinekinase, amylase, AST, ALT, ALP, albumin, bilirubin (total and direct), LDH.
- 9. In patients from 4 years of age and when applicable according to the judgment of treating physician.
- 10. In patients *below* 4 years of age and when applicable according to the judgment of treating physician.
- 11. Adverse Events /Adverse Drug Reactions based on all risk categories associated with Lamzede EU RMP, including infusion related reactions (IRRs) and hypersensitivity (as identified risks), acute renal failure, loss of consciousness and medication errors (as potential risks). Data on pregnancy and lactation (as missing information) will be also collected if available.
- 12. One of the Behavior Checklists (CBCL prescholar-scholar, ABCL/ASR (self-reporting), OABCL) will be used to the applicable age and according to the judgment of treating physician.

9.3 Variables

Only available evaluations as decided by the treating physician based on local routine clinical practice will be collected in the Registry. Patients' retrospective data may be collected if available. Where there are no data to report, this will be indicated in the applicable section(s) of the eCRF. See Table 1 for the schedule of assessments to be reported.

9.3.1 Demographic and Baseline Characteristics

After the patient, or parents or a legally acceptable representative according to local regulation, has provided signed informed consent and the patient has been included in the Registry, the following information will be reported in the eCRF for the baseline visit.

- Demographics (ethnicity, age, gender).
- Medical and disease history and concomitant illnesses includes collection of time to diagnosis and manifestations, infections/fractures (if any), blood genotype results, serum/leukocyte determination of disease activity level, residual enzymatic activity, occurrence of bone marrow transplantation and outcome, hepatic or renal insufficiency.
- Previous and concomitant medications, including Lamzede received in hospital or home infusion setting*.
- Previous and concomitant procedures.
- Physical examination (including ability to perform the endurance test).
- Vital signs [systolic (SBP) and diastolic blood pressure (DBP), pulse rate (PR)] and anthropometric measurements (weight, height, head circumference with rate of growth by gender and age when applicable).

*all available information regarding therapies received by the patient before inclusion in the current study

Clinical Protocol Number: CLI-LMZYMAA1-12

Clinical Protocol Version Number: 8.0

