Figure 1 Alpha-Mannosidosis Treatment Response Models Treatment Response Model

Chiesi	
Clinical Protocol Number: CLI-LMZYMAA1-12	
Clinical Protocol Version Number: 8.0	Date: 01 February 2019

Source: Provided by Chiesi

Based on the MCID-based Treatment Response Model, the Global Response to Treatment (GRT) of rhLAMAN-05 shows a discernible treatment difference between the two groups, with a clinical response in at least two domains at 12 months observed in 87% of patients treated with velmanase alfa compared to 30% in placebo. Moreover, 13% treated patients but none of the placebo patients reported a clinically-significant response in all three domains (Figure 3).

In the single-arm, integrated analysis from rhLAMAN-10 study, a remarkably similar proportion of 79% of patients showed a significant response in at least two domains at 12 months, 24% in all three. The proportion increases at Last Observation with a clinically meaningful response in at least two domains achieved in 88% patients (100% of paediatric patients and 71% of adult patients) and in at least three domains in 45% patients (53% of paediatric patients and 36% of adult patients) (Figure 2). The proposed domains are aligned with the representation of (a) the clinical burden, (b) the endpoints hierarchy defined with the CHMP, (c) the measurements of the benefit perceived by the patients (health-related QoL).

Figure 2 Global Response to Treatment in rhLAMAN-10 Study Integrated Analysis

Collesi	
Clinical Protocol Number: CLI-LMZYMAA1-12	
Clinical Protocol Version Number: 8.0	Date: 01 February 2019

The most common adverse reactions observed during treatment with Lamzede were weight increase (18%), infusion-related reactions (9%), diarrhoea (12%), headache (9%), arthralgia (9%), increased appetite (6%) and pain in the extremities (6%). A total of two serious adverse reactions (loss of consciousness in one patient and acute renal failure in one patient) considered possibly related to study treatment were observed; both cases recovered without sequelae. For further safety information, refer to the Lamzede SmPC.

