8. RESEARCH QUESTION AND OBJECTIVES

Primary Objective

- To assess the long-term effectiveness and safety of treatment with Lamzede under conditions of routine clinical care.
- In terms of effectiveness, the primary focus of the registry is to estimate the Global Treatment Response rate as percentage of patients qualified as responders by aggregately assessing oligosaccharides in serum (umol/L), (GTR-Pharmacodynamic Domain), 3MSCT (step/min), 6MWT (mt), FVC (% of predicted) (GTR-Functional Domain) and QoL based on CHAQ VAS-Pain and CHAQ- Disability Index (GTR-QoL Domain).
- In terms of safety, the rate of AEs (including ADA, IRRs and Hypersensitivity as identified risks) in the treated patients will be the main research of the study.

Secondary Objectives

- To characterize the alpha-mannosidosis population, including clinical manifestation, progression and natural history.
- In particular, oligosaccharides in serum (umol/L), endurance based on 3MSCT (step/min), 6MWT (m) and 2MWT (m) assessment, respiratory function through FVC (as litre and as percentage of predicted), hearing function with PTA, length and rate of infections (requiring or not antibiotics), rate of psychotic events, immunological status as per serum IgG, IgA and IgM, and QoL assessed by EQ-5D-5L, Zarit Burden Interview, CHAQ, Behavior Checklists (prescholar, scholar, adult and older adult) will be adopted for characterizing the alpha-mannosidosis population
- Rate of incidence of acute renal failure and loss of consciousness (as potential risks under Lamzede treatment), change in vital signs (SBP, DBP), laboratory tests (haematology and chemistry), physical examination and ECG will also be monitored.

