9.3.3 Assessments

For the baseline visit and each follow-up routine clinical visit the following information will be reported in the eCRF if considered necessary and available as part of routine clinical practice by the treating physician:

- Genetic mutations testing, residual enzymatic activity (at Baseline only).
- Anti-velmanase alfa-IgG antibody (ADA) test in serum*. Only for patients receiving Lamzede treatment, at Baseline for patients about to start Lamzede therapy. Additional measurements will follow the judgment of the treating physicians.
- Laboratory chemistry and standard haematological if available per clinical practice:
 - Hemoglobin, hematocrit, platelet count, red blood cells, white blood cells with differential count (band forms, segment forms, neutrophils, eosinophils, basophils, monocytes, lymphocytes) (all expressed in % as well as in absolute numbers). Blood smear for leukocytes detection by electronic microscopy may be done at the treating physician's discretion.
 - Biochemistry: Serum electrolytes (sodium, potassium, calcium, inorganic phosphate), creatinine, creatine-kinase, amylase, AST, ALT, ALP, albumin, bilirubin (total and direct), LDH.
- Oligosaccharides in serum*
- 3MSCT (annually, see Section 9.3.3.3 for further details of the 3MSCT), when applicable.
- 6MWT (annually, see Section 9.3.3.3 for further details of the 6MWT), when applicable.
- 2MWT (annually, see Section 9.3.3.3 for further details of the 6MWT), when applicable
- FVC, as litre and as percentage of predicted, annually, when applicable.
- Serum IgG and IgA*
- Serum IgM.
- Electrocardiogram (ECG) (annually; more frequently in treatment-naive patients if considered necessary by the treating physician).
- Hearing test (by pure tone audiometry [PTA]) (annually).
- Occurrence of infections, antibiotic treatment requirement and length of treatment.
- Occurrence of psychotic events.
- Occurrence of all AEs/ADRs based on all risk categories associated with Lamzede EU RMP, including non-serious and Serious AEs, ADRs, AEs leading to treatment discontinuation and AEs leading to death at any time they become available.

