11.7 Outcome

Each AE must be rated by choosing among:

- Recovered/resolved.
- Recovering/resolving.
- Not recovered/not resolved.
- Recovered with sequelae/resolved with sequelae.
- Fatal.
- Unknown.

Clinical Protocol Number: CLI-LMZYMAA1-12

Clinical Protocol Version Number: 8.0

11.8 Recording of Adverse Events

All AEs occurring during the course of the study must be documented in the AE page of the eCRF. Moreover, if the AE is related to the study drug, the AE form must be also completed.

It is responsibility of the investigator to collect all AEs (both serious and non-serious) derived by spontaneous, unsolicited reports of patients, by observation and by routine open questionings.

The recording period for AEs is the period starting from the Informed Consent signature until the patient's study participation ends.

If a clinically significant abnormal laboratory finding or other abnormal assessment meets the definition of an AE, then the AE eCRF page must be completed, as appropriate. A diagnosis, if known, or clinical signs and symptoms if diagnosis is unknown, rather than the clinically significant abnormal laboratory finding, should be reported on AE eCRF page. If no diagnosis is known and clinical signs and symptoms are not present, then the abnormal finding should be recorded.

In order to collect as complete as possible information in the clinical study database, all ADRs and SAEs ongoing at the time the patient's study participation ends should be evaluated up to 14 days after last study drug intake. After this period, all unresolved ADRs and SAEs will be reported as "ongoing" in the eCRF.

For pharmacovigilance purposes, all SAEs should be followed-up in order to elucidate as completely and practically as possible their nature and/or causality until resolution of all queries, clinical recovery is complete, laboratory results have returned to normal, stable condition is reached or the patient is lost to follow-up. Follow-up may therefore continue until after the patient has left the study up to 30 days after his/her discontinuation from the study for unrelated SAEs, and without timelines for related SAEs.

11.9 Reporting Serious Adverse Events to Chiesi

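### Table 1 footnote 7 and Section 9.3.3 make adverse event recording conditional on the physician's judgement, while Section 11.8 requires every adverse event to be recorded

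*Protocol*

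**What the plan says.** Section 8 makes AEs the main safety question: "the rate of AEs (including ADA, IRRs and Hypersensitivity as identified risks) in the treated patients will be the main research of the study". Section 9.7.5 analyses them as proportions of patients at risk and as person-time rates, and Section 9.7.1 explains that rates will rest on person-years because time in the Lamzede safety set will vary widely.

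Two places in the methods set a condition on recording:

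- **Table 1 (Section 9.2.6).** The row "Adverse Events /Adverse Drug Reactions" belongs to the block headed Assessments, and that heading carries footnote 7: "All assessments mentioned in the above table will be collected only if considered necessary and available as part of routine clinical practice". The treating physician decides. The footnote makes no exception for any row.
- **Section 9.3.3.** The lead-in puts the same necessary-and-available condition over the whole list, and the last bullet of that list is adverse events: "Occurrence of all AEs/ADRs based on all risk categories associated with Lamzede EU RMP", followed by an explicit mention of serious and non-serious events.

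Section 11.8 sets no condition: "All AEs occurring during the course of the study must be documented in the AE page of the eCRF". It makes the investigator responsible for collecting serious and non-serious events, including through routine open questions, from consent to the end of participation.

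**The concern.** A duty to record every AE and a permission to record an AE only when it is thought necessary cannot both bind the same site. About 40 centres are foreseen, each patient is to be followed for 15 years, and the protocol does not rank the two instructions. A site that works from the flow-chart can omit an event and believe it has complied. A site that works from Section 11 cannot.

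What is at stake is the completeness of the main safety outcome. Omitted events lower the count but leave exposure unchanged, so the error runs in one direction. It could also differ between sites for reasons unrelated to the drug. Analysis could not repair it afterwards, because an event never entered leaves no trace in the database.

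**Working it through.** The protocol states no AE rate and no precision target for safety, so there is no figure to reproduce. The check is a comparison of texts, followed by an illustration on assumed values.

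**Step 1: does the condition reach AEs?** Footnote 7 attaches to the block heading and speaks of all assessments in the table. The AE/ADR row is in that block, alongside infections and psychotic events, which are not tests either. The 9.3.3 lead-in governs a list whose final bullet is AEs. Read literally, both conditions cover AEs.

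**Step 2: could the protocol have exempted them?** Yes. It words other items without the condition: Section 9.3.1 simply says that baseline information will be reported, and Table 1 footnote 6 says that weekly therapy data need to be recorded. AEs were placed under the conditional wording without such treatment.

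**Step 3: which events are exposed?**

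| Event type | Separate duty outside Table 1 and 9.3.3 | Exposed to the conditional wording? |
|---|---|---|
| SAE | 11.9: report within 24 hours | Largely protected |
| Non-serious ADR | 11.8: additional AE form; 11.10: report to authorities | Largely protected |
| Non-serious, unrelated AE | 11.8 only | Yes |

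**Step 4: would the loss be visible?** Section 9.3 says that an absence of data will be indicated in the eCRF. Section 9.9 says that where there are no data nothing is recorded. Under the latter, no AE and an AE not recorded can look the same. Section 9.7.5 counts withdrawn patients without events as event-free for the period, which does not separate the two cases.

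**Step 5: direction and illustrative size.** Let *s* be the share of person-time at sites that apply the conditional wording and *c* the share of AEs that those sites record. Other sites record everything, and true rates are taken as equal across sites. Then

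observed rate / true rate = (1 − s) + s × c.

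For example, s = 0.25 and c = 0.50 give 0.75 + 0.125 = 0.875. Neither *s* nor *c* is in the protocol; the grid below is assumption only.

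| s | c = 0.25 | c = 0.50 | c = 0.75 |
|---|---|---|---|
| 0.25 | 0.81 | 0.88 | 0.94 |
| 0.50 | 0.63 | 0.75 | 0.88 |
| 1.00 | 0.25 | 0.50 | 0.75 |

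Every cell is below 1. Because SAEs and ADRs are largely protected, a low *c* would need most AEs to be non-serious and unrelated. The formula applies to event rates per person-time. It does not carry over to the proportion of patients with at least one AE, since a patient who loses one event may still have another on record.

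**The case against.** The best defence is that the intent is clear enough. Footnote 7 closes by ruling out tests done only for the Registry, so its subject is probably tests. The AE row is the only one in its block marked at all five visit types. Item 3.5 of the ENCePP checklist, on how AEs are collected and reported, points to Section 11. Monitors check the eCRF against source documents (Section 9.8.2), and discrepancies are queried (Section 9.6).

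Most of this stands as evidence of intent, and it limits the weight of the point. It does not remove the conflict. A checklist pointer is not a precedence rule, and footnote 7 says all assessments. Source verification finds only events already written in the notes, and a monitor needs one agreed rule to query against.

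Three stronger readings are tempting and should not be drawn:

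- **That the risk management plan (RMP) categories act as a filter.** Footnote 11 reads "Adverse Events /Adverse Drug Reactions based on all risk categories associated with Lamzede EU RMP, including infusion related reactions (IRRs) and hypersensitivity", which might suggest that only RMP events are recorded. But it says including, the 9.3.3 bullet speaks of all AEs and names non-serious ones, and Section 9.7.5 lists the RMP risks separately from AEs. The wording is loose rather than restrictive.
- **That the loss can be sized from the common reactions in Section 7.1.** One might add up the percentages for reactions that footnote 11 does not name and call the sum the share lost. That fails three times. Footnote 11 is not the full RMP list, since Sections 8 and 9.7.5 treat ADA as an identified risk and footnote 11 omits it. Patient percentages overlap and are not shares of events. And these are adverse reactions, which carry the extra duties in Sections 11.8 and 11.10.
- **That the treated-versus-untreated contrast is distorted.** A site's reading would apply to both its treated and its untreated patients, several events named in footnote 11 can occur without Lamzede, and the contrast is exploratory in any case (Section 9.1).

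**Conclusion.** The contradiction is real and lies in current text. Footnote 7 and the 9.3.3 lead-in allow an AE to go unrecorded on the physician's judgement; Section 11.8 does not. If some sites follow the conditional wording, the AE rate in treated patients is biased downward, mainly through non-serious, unrelated events.

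The size cannot be derived from the protocol. The grid above shows direction and a range under assumed values and is not an estimate. The conclusion rests on at least some sites taking footnote 7 or the 9.3.3 lead-in at face value; if all follow Section 11.8, there is no bias. This is a wording conflict worth resolving before data collection starts, because unrecorded non-serious events may not be recoverable later. It does not undermine SAE or ADR reporting and does not make any planned analysis impossible.

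**What to change.** 1. **Footnote 7 and the 9.3.3 lead-in.** Add a sentence such as: *This condition applies to tests, procedures and questionnaires. It does not apply to adverse events, which are recorded for all patients as set out in Section 11.8.*
2. **Footnote 11 and the 9.3.3 AE bullet, as a clarification only.** Add: *The RMP categories flag events for reporting; they do not limit which events are recorded.*

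The cost is a few sentences. No test or visit is added, so the non-interventional character of the Registry is unaffected. The one downside is somewhat more AE entry at sites that would have used the conditional reading.
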